10.9.4 Visit 4 (Week 4)

Enrolled patients will return to the clinic 4 weeks (+/- 4 days) after completing Visit 2. The following assessments and evaluations will be carried out during these study visits:

- Assess disease activity scores:
 - BILAG-2004 index
- Collect, check and transcribe diary card into eCRF
- Record all AEs
- Record concomitant medication
- Perform complete physical examination, including body temperature and weight
- Measure vital signs – brachial pulse and blood pressure to be taken after 3 minutes of rest in a supine position prior to and 1 hour post study product administration
- Perform urinalysis, including dipstick and microscopic examination
- Perform urine pregnancy test for female patients of childbearing potential
- Obtain blood sample for:
 - Hematology, coagulation (INR, PT, PTT, fibrinogen), biochemistry (complete)
 - Anti-IFN α binding antibodies
 - Inflammatory markers (C3, C4, CH50)
- Check contraindications
- Administer study product (two syringes)
- Record solicited injection site reactions during one hour following study product administration
- Record solicited systemic AEs during one hour following study product administration
- Provide diary card for daily recording by the patient of solicited AEs (Day 1 to Day 7)

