5.2.4.5 Exploratory analyses

The following analysis will be performed on the FAS population except if otherwise specified.

5.2.4.5.1 **PGA scores**

PGA score at each visit and change from baseline by treatment group will be presented. (Statistical tables 14.2.28.1 to 14.2.28.2)

All PGA data will be listed in Listing 16.2.6.10.

5.2.4.5.2 **SLE flares**

Time to first SLE flare in patients will be analyzed using a cox regression model.

The first model will be adjusted on treatment group.

The second model will be performed only on patients IFN-K treated and will be adjusted on presence/absence of neutralizing antibodies. (Statistical tables 14.2.29.1 to 14.2.29.2)

5.2.4.5.3 **28-Tender and Swollen Joint Counts (SJC)**

28-Tender and Swollen Joint Counts and Joint Pain VAS at each visit and change from baseline will be presented. The changes at Week 36 will be analyzed using a t-test. (Statistical tables 14.2.30.1 to 14.2.32.2).

28-Tender and Swollen joint counts data will be listed in Listing 16.2.6.11, and joint Pain VAS data in Listing 16.2.6.12.

5.2.4.5.4 **Treatment failure**

- Proportion of treatment failure will be analyzed using frequency table methods. Patients will be considered as treatment failure if they receive more than 5 mg prednisone equivalent/day at any time between Week 24 (Visit 9) and Week 36 (Visit 12) or if their CS dose is increased above the Week 24 level is recorded (this criterion will be identified by medical review) (Statistical table 14.2.33)

5.2.4.5.5 **SF-36**

Statistical Analysis Plan

Study Name: IFN-K-002

SAP version & date: v4, 18/Jun/2018

Physical Component Summary (PCS) and Mental Component Summary (MCS) scores at each visit and change from baseline will be presented. The changes at Week 36 will be analyzed using a non-parametric Wilcoxon rank sum test (Statistical tables 14.2.34.1 to 14.2.35.2). If one is statistically significant then the individual domain scores will also be described.

In addition, number of patients with clinically meaningful improvements \geq Minimum Clinically Important Differences (MCID) of 2.5 points for summary and 5.0 points for domain scores between baseline and Week 36 will be presented. (Statistical tables 14.2.36 to 14.2.37)

All SF-36 data will be presented in Listing 16.2.6.13.

5.2.4.5.6 **FACIT**

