- TEAEs by SOC, PT and status of IFN α neutralizing antibodies (positive/negative) at time of event (only on patients IFN-K treated) (Statistical Tables 14.3.7.7 to 14.3.7.10)
- TEAEs by SOC, PT and relationship (Statistical Tables 14.3.8.1 to 14.3.8.6)
- TEAEs by SOC, PT and intensity (Statistical Tables 14.3.9.1 to 14.3.9.6)
- TEAEs leading to permanent study treatment discontinuation by SOC and PT (Statistical Table 14.3.10) (only throughout the study)
- SAEs by SOC and PT (Statistical Tables 14.3.11.1 to 14.3.11.7)
- SAEs by SOC, PT and status of IFN α neutralizing antibodies (positive/negative) at time of event (only on patients IFN-K treated) (Statistical Tables 14.3.11.8 to 14.3.11.11)
- SAEs by SOC, PT and relationship (Statistical Tables 14.3.12.1 to 14.3.12.7)
- SAEs by SOC, PT and intensity (Statistical Tables 14.3.13.1 to 14.3.13.7)
- SAEs leading to permanent study treatment discontinuation by SOC and PT (Statistical Table 14.3.14)

The following rules will be applied to analyze the occurrence of AE according to the status of IFN α neutralizing antibodies (positive/negative):

- For adverse event which occurred between dose 1 and dose 3 included, status of neutralizing capacity will not be assessed
- For adverse event which occurred between 3rd dose (excluded) and Visit 6 (included), status of neutralizing capacity at visit 6 will be used
- For adverse event which occurred between Visit 6 (excluded) and Visit 9 (included), status of neutralizing capacity at visit 9 will be used
- For adverse event which occurred between Visit 9 (excluded) and Visit 12 (included), status of neutralizing capacity at visit 12 will be used

Statistical Analysis Plan

Study Name: IFN-K-002

SAP version & date: v4, 18/Jun/2018

Statistical Analysis Plan

Study Name: IFN-K-002

SAP version & date: v4, 18/Jun/2018

Adverse events listings:

All adverse events (including solicited local and systemic reactions) recorded during the study will be presented in Listings. The following information (if available) will be included in the listings (non-exhaustive list):

- Patient identifier
- Age, Ethnic origin (see section 9 Derived data), gender, weight
- The adverse event (System organ class, preferred term, reported term)
- Start date, end date, duration, period
- Severity (e.g., mild, moderate, severe)
- Seriousness (serious/non-serious)
- Action taken
- Outcome
- Relatedness assessment

Listings will be provided for:

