7.5 LLDAS

Analysis for LLDAS, initially not planned in the protocol, will be done.

8 Software documentation

All summaries and statistical analyses will be generated using SAS version 9.4 or higher.

Statistical Analysis Plan

Study Name: IFN-K-002

SAP version & date: v4, 18/Jun/2018

9 Derived data

Derived variable	Derivation algorithm
Change from baseline to visit V (continuous)	
Change from baseline of variable X=X(Visit V)-X(Baseline)
 
 ○ Negative values indicate a decrease in X ○ Positive values indicate an increase in X
Percent change from baseline to visit V (continuous)	
Percent change from baseline of variable X=100 *[X(Visit V)-X(Baseline)]/X(Baseline)
 
 ○ Negative values indicate a decrease in X ○ Positive values indicate an increase in X
Treatment Compliance (continuous)	
The compliance Ci for patient i will be computed according to:
 $C_i = \frac{D_i^t * 100}{D_i^p}$ 
where D_i^p mg is the total amount (mg) of IP prescribed to patient i and D_i^t is the total amount (mg) of IP actually taken by the patient during the study i.e., before the end of study for patient i.

Treatment compliance (categorical) (if relevant)	
Categorial variable with three modalities:
 
 • $C_i < 80\%$ • $80\% \leq C_i < 120\%$ • $C_i \geq 120\%$
Event Duration	$(\text{End Date}) - (\text{Start Date}) + 1$
BILAG score	See BILAG-2004 Index scoring
SLEDAI-2K and SELENA SLEDAI	Sum of the weights
SLICC/ACR	Sum of items
CLASI	Sum of items
FACIT	See FACIT-Fatigue Subscale Scoring Guidelines (Version 4)

Statistical Analysis Plan

Study Name: IFN-K-002

SAP version & date: v4, 18/Jun/2018

Derived variable	Derivation algorithm
SF-36	See SF-36 Health Survey, Manual and Interpretation Guide
Time to event SLE flare	
SLE flare will be identified in BILAG-2004 scoring.
 
SLE flares are predefined as a BILAG A or B score due to items that were new or worse in any of the eight organ system (Isenberg et Al).
 
For patient with a SLE flare: Time to event = Visit date of corresponding BILAG – Date of Week 0 + 1
 
For patient without SLE flare: Time to event = Date of Week 36 (or date of end of study for patients prematurely withdrawn before Week 36) – Date of Week 0 +1

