14.2.21	Immunogenicity analysis - Anti-IFN α binding antibodies - GMT				X	
14.2.22	Immunogenicity analysis - Anti-IFN α antibody neutralizing capacity (NC50) - Positive antibody response over time				X	
14.2.23	Immunogenicity analysis - Log-transformed NC50 for anti-IFN α neutralizing antibodies				X	
14.2.24	Immunogenicity analysis - Anti-IFN α neutralizing antibodies - GMT				X	
14.2.25	Immunogenicity analysis - Anti-KLH binding antibody titers - Positive antibody response over time				X	
14.2.26	Immunogenicity analysis - Log-transformed dilution titers for anti-KLH binding antibodies				X	
14.2.27	Immunogenicity analysis - Anti-KLH binding antibodies - GMT				X	
14.2.28.1	Exploratory analysis - PGA score - Value at each visit			X		
14.2.28.2	Exploratory analysis - PGA score - Change from baseline			X		
14.2.29.1	Exploratory analysis - SLE Flare - Cox model adjusted on treatment group			X		
14.2.29.2	Exploratory analysis - SLE Flare - Cox model adjusted on presence/absence of neutralizing antibodies			X		
14.2.30.1	Exploratory analysis - 28-Tender joints counts - Value at each visit			X		
14.2.30.2	Exploratory analysis - 28-Tender joints counts - Change from baseline			X		
14.2.31.1	Exploratory analysis - 28-Swollen joints counts - Value at each visit			X		
14.2.31.2	Exploratory analysis - 28-Swollen joints counts - Change from baseline			X		
14.2.32.1	Exploratory analysis - Joint Pain VAS - Value at each visit			X		
14.2.32.2	Exploratory analysis - Joint Pain VAS - Change from baseline			X		
14.2.33	Exploratory analysis - Treatment failure			X		
14.2.34.1	Exploratory analysis - SF-36 - Physical Component Summary (PCS) - Value at each visit			X		
14.2.34.2	Exploratory analysis - SF-36 - Physical Component Summary (PCS) - Change from baseline			X		

Statistical Analysis Plan

Study Name: IFN-K-002

SAP version & date: v4, 18/Jun/2018

Number	Title	Screened	SAF	FAS	PP	Other
14.2.35.1	Exploratory analysis - SF-36 - Mental Component Summary (MCS) - Value at each visit			X		
14.2.35.2	Exploratory analysis - SF-36 - Mental Component Summary (MCS) - Change from baseline			X		
14.2.36	Exploratory analysis - Clinically meaningful improvements - Physical Component Summary (PCS)			X		
14.2.37	Exploratory analysis - Clinically meaningful improvements - Mental Component Summary (MCS)				X	
14.2.38	Exploratory analysis - Clinically meaningful improvements - Domains			X		
14.2.39.1	Exploratory analysis - FACIT total score - Value at each visit				X	

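### The exploratory Cox model of time to first flare does not say when neutralising-antibody status is taken; coded as one fixed value, it can show false protection

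*SAP*

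**What the plan says.** SAP 5.2.4.5.2 states: "Time to first SLE flare in patients will be analyzed using a cox regression model". The first model compares the randomised groups. For the other, "The second model will be performed only on patients IFN-K treated", and it "will be adjusted on presence/absence of neutralizing antibodies". The table list in SAP 10.1 (table 14.2.29.2) says only "Cox model adjusted on presence/absence of neutralizing antibodies". Neither place gives a visit, a landmark or time-dependent coding. SAP section 9 (Derived data) defines the flare time but has no entry for antibody presence. SAP 5.2.4.4.2 gives the positivity cut-off (NC50 of at least 200) but no time point for this model.

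The event and clock are clear. In SAP section 9, "SLE flares are predefined as a BILAG A or B score due to items that were new or worse" in an organ system, and the event time runs from Week 0 to the "Visit date of corresponding BILAG". Protocol 10.9.4 lists the "BILAG-2004 index" at Week 4, and it recurs every four weeks to Week 36. The first post-baseline neutralising sample is at Week 12 (Protocol 10.9.6); Weeks 4 and 8 list binding antibodies only.

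Elsewhere the SAP does fix a time. Week 36 status is named for the antibody models of the co-primary endpoints (5.2.4.2) and SRI-4 (5.2.4.3.1), and 5.2.5.2 gives interval-specific status for adverse events. No such rule covers the flare model.

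**The concern.** In the earlier study no subject had neutralising activity at baseline (Protocol 5.4.3), so positive status is acquired during follow-up. A single presence/absence term divides patients from Week 0 by something learned at Week 12 or later. If a flare makes it less likely that a patient is later seen to be positive, flaring patients collect in the negative group and antibodies look protective.

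The documents make such a link plausible. Listed medications stop study product (Protocol 10.7.2). In the earlier 120 mcg group, neutralising antibodies were seen only in the three patients given four administrations (Protocol 5.5), and here the fourth is at Week 12. A patient who leaves has status frozen at the last sample.

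At stake is how the flare hazard ratio would be read as evidence that neutralisation matters clinically. Relating immune to clinical responses is a stated exploratory objective (SAP 2.2.3).

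**Working it through.** The documents give no event count, hazard ratio or power for this model, so there is no figure to reproduce.

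**Inputs from the documents.** Nine post-baseline BILAG visits, Weeks 4 to 36; first post-baseline neutralising sample at Week 12; 89 IFN-K patients enrolled, 80 evaluable, 10% drop-out (SAP 2.3.2); two-sided 5% tests (SAP 5.1.2); neutralising antibodies in 4 of 5 patients at 240 mcg (Protocol 5.5).

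**Assumed, not in the documents.** Flare risk F by Week 36; share ever positive and its timing; share q of first flares after which no later conversion is seen. The true hazard ratio is 1 throughout.

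**Step 1: flares before status can be known.** With a constant hazard over nine visits, h = 1 - (1 - F)^(1/9). The share of first flares at or before Week 12 is [1 - (1 - h)^3]/F = [1 - (1 - F)^(1/3)]/F.
- F = 0.3: (1 - 0.888)/0.3 = 0.37
- F = 0.5: (1 - 0.794)/0.5 = 0.41
- F = 0.7: (1 - 0.669)/0.7 = 0.47

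So 37-47% of first flares fall when no earlier sample could have classed anyone as positive.

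**Step 2: ever positive, no flare-linked loss.** If eventual status is fully observed and unrelated to flare time, both groups share one flare-time distribution and the hazard ratio is 1. Simulation gives 0.99 to 1.01 in large samples, and 1.02 with 89 patients and F = 50%.

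**Step 3: ever positive, some flaring patients lost.** With 89 patients, F = 50% and loss at the flare visit:

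| Flaring patients lost | Share of arm | Null HR | False protection |
|---|---|---|---|
| 10% | 0.10 × 0.50 = 5% | 0.84 | 9% |
| 15% | 0.15 × 0.50 = 7.5% | 0.72 | 18% |
| 30% | 0.30 × 0.50 = 15% | 0.59 | 37% |

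The nominal rate of false protection is 2.5%. The first two rows lie within the planned 10% drop-out; the third exceeds it.

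A wider grid used F of 30-70%, 50% or 80% ever positive, and early, middle or late conversion. There q counts product stops as well as withdrawals. The null hazard ratio was 0.80-0.95 at q = 10% and 0.61-0.86 at q = 25%.

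**Step 4: status read at the flare or censoring visit.** A patient who flares early has had little time to convert, whereas a patient who is flare-free to Week 36 has had all of it. On the same grid the null hazard ratio is 0.19 to 0.54 whatever q is. With 80 patients, 80% ever positive and F of 30-50%, 87-98% of trials show false protection.

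**Step 5: time-dependent status.** Each patient counts as negative until a positive sample has been taken, and that sample applies only to later visits. The null hazard ratio is 0.99 to 1.02 in every scenario. False protection with 80 or 89 patients is 2.2-3.0%. Because only the first flare counts, whatever happens to sampling afterwards cannot enter the model.

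**The case against.** A reader might infer that the SAP prescribes a fixed covariate. It does not: the word does not appear. The gap is an undefined time point and coding, with a fixed value as the default reading of a single term.

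A reader might also infer that starting the clock before antibodies appear is enough to create the bias. It is not. A flare does not end follow-up. Patients who stop product are encouraged to continue to Week 36 (Protocol 10.6.3, 10.7.2), and step 2 then gives a hazard ratio of about 1. The bias needs flare-linked loss of doses or samples, or status read at the event.

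Safeguards reduce the loss. The early termination visit includes a neutralising sample whenever possible (Protocol 10.9.13). The flare definition takes in any new or worse BILAG B, while the list of medications that stop product is narrow, so many flares would not trigger it. At 15% of flaring patients withdrawing (F = 50%, 89 patients), one set of runs gave 0.76 with no termination sample, 0.80 with one at the flare visit, and 0.86 if withdrawal came eight weeks later (an assumed delay); false-positive rates were 15%, 11% and 10%. This shrinks the bias but does not remove it, and it does nothing for the step 4 reading.

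It is also tempting to fault the adverse-event tables. The documents do not support that for early events: "For adverse event which occurred between dose 1 and dose 3 included, status of neutralizing capacity will not be assessed". That rule avoids assigning a status before one is measured. It should not be copied unchanged into the Cox model, because later events take their status from the next visit.

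Finally, the model is exploratory and lies outside the success rule (SAP 5.2.4.1) and the testing sequence (SAP 5.3.5). That stands and limits the consequence.

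**Conclusion.** The point holds in conditional form. The SAP leaves the timing and coding of neutralising status open in a model where the choice moves the null hazard ratio from about 1.0 to about 0.2.

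- Ever positive, complete sampling to Week 36, status unrelated to flare: no bias.
- Ever positive, 10-15% of flaring patients lost: about 0.7 to 0.85, assuming 30-50% flare risk and 30/60/80% positive by Weeks 12/24/36.
- Status at the flare or censoring visit: about 0.2 to 0.5 without any loss.

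Larger losses give stronger effects. At 50% flare risk, however, withdrawal of 30% or more of flaring patients would exceed the planned drop-out, so those figures are upper ranges. Using Week 36 status, as the other antibody models do, was not simulated; it also looks ahead, and patients without that sample have no status. The co-primary conclusions are unaffected. The change is worth making because the better method is specific and cheap, and the SAP is meant to settle such choices before unblinding.

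**What to change.** In SAP 5.2.4.5.2, table 14.2.29.2 and section 9, state that neutralising status enters as a time-dependent covariate taken from the last sample before each risk time, and is negative until the first positive sample (NC50 of at least 200). A sample drawn at the visit where a flare is scored should count only for later visits. State how a later negative sample is handled. Describe the result as a non-randomised association within the IFN-K arm, since patients who convert may differ in other ways.

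A Week 12 landmark is at most a sensitivity analysis. It drops earlier flares, and on the assumed conversion rates (80 - 30)/(100 - 30) = 71% of Week 12 negatives would convert later.

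The cost is SAP wording and a few lines of code; no new data are needed.

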13.9.6 Analysis of the Exploratory Endpoints

- Clinical response by assessing disease activity using: 28-Tender and Swollen Joint Counts and Joint Pain VAS will be analyzed using a t-test
- Number of SLE flares will be analyzed using frequency table methods
- Time to first SLE flare in patients will be analyzed using life-table methods
- Proportion of patients with an increase or addition in lupus therapy will be analyzed using frequency table methods

- Proportion of treatment failure will be analyzed using frequency table methods. Patients will be considered as treatment failure if they receive more than 5 mg prednisone equivalent/day at any time between Week 24 (Visit 9) and Week 36 (Visit 12) or if their CS dose is increased above the Week 24 level or if any increase of immunosuppressive treatment between Week 12 and Week 36 above CS dose at Week 12 is recorded.
- Changes in the SF-36 score: Physical Component Summary (PCS) and Mental Component Summary (MCS) scores using non-parametric Wilcoxon-test; if one is statistically significant then the individual domain scores will also be analyzed. Also clinically meaningful improvements \geq Minimum Clinically Important Differences (MCID) of 2.5 points for summary and 5.0 points for domain scores will be analyzed
- Quality of life using FACIT fatigue score will be analyzed using a t-test
- Changes in the levels of auto-antibodies (anti-dsDNA, anti-Smith antigen [anti-Sm], anti-RNP, anti-SSA/Ro, anti-SSB/La, anti-cardiolipin, and anti- β 2-glycoprotein I antibodies) will be analyzed using a t-test
- Changes in the levels of biomarkers (C3, C4, CH50) will be analyzed versus baseline
- Anti-IFN α and anti-KLH antibody isotyping
- Anti-Hemagglutinin antibody response: seroconversion (four fold increase in antibody titers post-vaccination) and seroprotection (HIA antibody titers \geq 1:40 post-vaccination)
- Correlation between immunogenicity responses and clinical or biological parameters will be performed on an exploratory basis

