4.1 Efficacy endpoints

4.1.1 Primary efficacy endpoint(s)

Two co-primary endpoints are evaluated in the trial:

- Change from baseline in the expression of IFN-induced genes at Week 36.
- Response to treatment with IFN-K as measured by the British Isles Lupus Assessment Group (BILAG)-based Composite Lupus Assessment (BICLA) response criteria at Week 36:
 - All BILAG A scores at baseline improve to B/C/D and all BILAG B scores improve to C/D at Week 36
and
○ No BILAG worsening in other body systems: no new BILAG A or ≥ 2 new BILAG B scores at Week 36
and
○ No worsening in SLEDAI-2K total score at Week 36 compared with baseline
and
○ No deterioration in PGA (< 10% worsening) on VAS 100 mm at Week 36 compared with baseline
and
○ No addition or increased dose level of anti-malarial drugs or immunosuppressive drugs or corticosteroids between Week 24 and Week 36 (this criterion will be identified by medical review)

Statistical Analysis Plan

Study Name: IFN-K-002

SAP version & date: v4, 18/Jun/2018

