4.1.3 Exploratory efficacy endpoints

- Evaluation of clinical response by assessing disease activity using:
 - PGA scores,
 - number of SLE flares,
 - Time to first SLE flare in patients post randomization,

Statistical Analysis Plan

Study Name: IFN-K-002

SAP version & date: v4, 18/Jun/2018

- 28-Tender and Swollen Joint Counts (SJC),
- Joint Pain VAS
- the incidence of an increase or addition in lupus therapy (intensification and/or add of drugs). (this criterion will be identified by medical review)
- Quality of life using:
 - FACIT fatigue score
 - Changes in the SF-36 score: Physical Component Summary (PCS) and Mental Component Summary (MCS) scores
- Evaluation of biological response by assessing:
 - Changes in the levels of auto-antibodies (ANA, anti-dsDNA, anti-Smith antigen [anti-Sm], anti-RNP, anti-SSA/Ro, anti-SSB/La, anti-cardiolipin, and anti-β2-glycoprotein I antibodies)
 - Changes in levels of biomarkers (C3, C4, CH50)
 - Anti-IFN α and anti-KLH antibody isotyping
 - Neutralizing Anti-IFN α antibodies towards IFN α subtypes
 - IFN β and IFN ω cross neutralization
 - Anti-Hemagglutinin antibody response

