SAP version & date: v4, 18/Jun/2018

The BILAG global score will be defined as the summation of the numerical values for the nine-system scores as given by the following formula:

$$\text{Numerical global score (xs)} = A*12 + B*8 + C*1$$

Where A, B and C represent the number of Grades A, B and C respectively at each assessment. Grades D and E are considered as 0 (Chee-Seng Yee *et al*, 2010).

All BILAG data will be listed in Listing 16.2.6.3.

5.2.4.3.4 *SELENA SLEDAI flare index*

The numbers of patients with a mild or moderate, or severe SLE flare (SELENA-SLEDAI flare index) and corresponding number of SLE flare will be presented. (Statistical table 14.2.13).

The total score at each visit (planned in the protocol) and change from baseline by treatment group will also be presented. The change at Week 36 will be analyzed using a t-test. (Statistical tables 14.2.14.1 to 14.2.14.2).

All SELENA-SLEDAI flare index data will be listed in Listing 16.2.6.4.

5.2.4.3.5 *SLICC/ACR-DI*

Total score at each visit and change from baseline by treatment group will be presented. The change at Week 36 will be analyzed using a t-test. (Statistical tables 14.2.15.1 to 14.2.15.2).

All SLICC/ACR-DI data will be listed in Listing 16.2.6.5.

5.2.4.3.6 *CLASI*

Total activity score and Total damage score at each visit and change from baseline by treatment group will also be presented. The changes at Week 36 will be analyzed using a t-test. (Statistical tables 14.2.16.1 to 14.2.17.2).

All CLASI data will be listed in Listing 16.2.6.6.

5.2.4.3.7 *LLDAS*

Number of patients achieving a LLDAS at Week 36 will be presented by treatment group (Statistical table 14.2.18). It is defined as:

- SLEDAI-2K ≤ 4 , with no activity in major organ systems (renal, CNS, cardiopulmonary, vasculitis, fever) and no haemolytic anaemia or gastrointestinal activity
- No new features of lupus disease activity compared with the previous assessment (New feature is defined as any BILAG item recorded as "new" (modality 4) at Week 36)
- Physician global assessment (PGA, scale 0–3) ≤ 1
- Current prednisolone (or equivalent) dose ≤ 7.5 mg daily (this criterion will be identified by medical review)
- Well tolerated standard maintenance doses of immunosuppressive drugs and approved biological agents, excluding investigational drugs (this criterion will be identified by medical review)

Statistical Analysis Plan

Study Name: IFN-K-002

SAP version & date: v4, 18/Jun/2018

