7.2.2 Secondary efficacy & exploratory analyses

The criterion “composite SRI-4 response (tapering CS \leq 5mg and \leq 7.5mg)”, initially not planned in the protocol, will be analyzed (same method as SRI-4).

The analysis on exploratory endpoint “changes in Lupus Therapy” has been removed because it is redundant with the BICLA and LLDAS analyses.

Statistical Analysis Plan

Study Name: IFN-K-002

SAP version & date: v4, 18/Jun/2018

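### The SAP's treatment-failure rule silently drops the protocol's Week 12–36 immunosuppressant-increase component, and the related therapy-change analysis was removed for a redundancy that does not hold

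*SAP*

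**What the plan says.** Protocol 13.9.6 counts a patient as a treatment failure on any one of three grounds. The first is more than 5 mg/day prednisone equivalent at any time from Week 24 to Week 36. The second is a rise in corticosteroid dose relative to Week 24. The third is worded as follows: "or if any increase of immunosuppressive treatment between Week 12 and Week 36 above CS dose at Week 12 is recorded".

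SAP 5.2.4.5.4 repeats the first two grounds and ends with "or if their CS dose is increased above the Week 24 level is recorded". The third ground is absent. The last two words do not fit the shortened sentence and match the end of the protocol's third clause.

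The protocol also plans a separate exploratory analysis in 13.9.6: "Proportion of patients with an increase or addition in lupus therapy will be analyzed using frequency table methods". SAP 7.2.2 says that the analysis of changes in lupus therapy "has been removed because it is redundant with the BICLA and LLDAS analyses". Yet SAP 2.2.3 keeps changes in lupus therapy as an exploratory objective, and SAP 4.1.3 keeps as an endpoint "the incidence of an increase or addition in lupus therapy (intensification and/or add of drugs", to be identified by medical review. No analysis section and no entry in the SAP 10.1 table list corresponds to it.

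SAP Section 7, which lists departures from the protocol's statistical sections, does not mention the narrower failure definition.

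**The concern.** Two changes remove the same kind of information. The failure rule loses its only component with a window that opens before Week 24, and the table that would have shown therapy increases by arm is withdrawn. The first change is undeclared, so a reader of Table 14.2.33 would take it for the protocol's endpoint. The second is declared, but with a reason that has to be tested.

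Background escalation matters when Week 36 responses are read. A patient whose immunosuppressant was raised at, say, Week 16 could be a responder at Week 36 partly for that reason. SRI-4 has no medication criterion, and the composite SRI-4 adds only oral corticosteroids (SAP 4.1.2.1). SAP 5.2.4.3.1 nevertheless says that SRI-4 could become the primary endpoint for further development. A by-arm record of who escalated, and when, is needed to interpret such results.

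**Working it through.** The plan gives no figure to reproduce. The check sets each rule against its window and asks what it counts between Weeks 12 and 24.

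| Rule | Source | Window | Counts a dose increase of existing MTX, AZA or MMF in Weeks 12–24? |
|---|---|---|---|
| Treatment failure, protocol, third ground | Protocol 13.9.6 | Weeks 12–36 | Yes, if read as an immunosuppressant rule |
| Treatment failure, SAP | SAP 5.2.4.5.4 | Week 24 onward, corticosteroids only | No |
| BICLA medication item | SAP 4.1.1 | Weeks 24–36 | No |
| LLDAS medication items | SAP 5.2.4.3.7 | Status at Week 36 | No |
| SELENA-SLEDAI flare index, medication items | Protocol Appendix 4 | Assessed at Weeks 24 and 36; look-back for these items not stated | No |

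**BICLA.** The item reads "No addition or increased dose level of anti-malarial drugs or immunosuppressive drugs or corticosteroids between Week 24 and Week 36". An increase made before Week 24 and then held passes it. Even inside its window, it is one of five criteria, so the BICLA response rate does not give the proportion who escalated.

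**LLDAS.** The relevant item is "Well tolerated standard maintenance doses of immunosuppressive drugs and approved biological agents, excluding investigational drugs". It asks what the patient is taking at Week 36, not whether the dose rose from an earlier level. The prednisolone item is likewise a current dose.

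**Flare index.** Its medication items are prednisone increases, added NSAID or hydroxychloroquine, and new cyclophosphamide, azathioprine or methotrexate. None is a dose increase of a drug already in use, and mycophenolate mofetil is not named.

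**Time to first flare.** This is derived from BILAG grades (SAP Section 9), with no medication item.

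**Window arithmetic.**
- Protocol third ground: 36 − 12 = 24 weeks.
- Part in which BICLA would register an immunosuppressant increase: 36 − 24 = 12 weeks.
- Remainder: 24 − 12 = 12 weeks, and 12/24 = 50% of that ground's window.

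**Effect on the proportion.** The grounds are joined by *or*. Removing one can only shrink the set of failures, so in each arm the SAP proportion is at most the protocol proportion. How much smaller, and whether the arms differ, cannot be worked out from the documents.

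**The case against.** A reader might infer that escalation between Weeks 12 and 24 is counted in no analysis. The documents do not support that:

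- The flare index is assessed at Week 24 and analysed in Table 14.2.13. It can register prednisone increases, added hydroxychloroquine and new azathioprine, methotrexate or cyclophosphamide.
- Protocol Table 4 does not permit starting antimalarials, MTX, AZA or MMF, or increasing corticosteroids, in the Maintenance Period. Such events would be protocol deviations, which SAP 5.2.2 tabulates by arm. Forbidden medication may also lead to exclusion from the per-protocol set (SAP 3.1.1).
- Medications are tabulated by arm (SAP 5.2.3 and the concomitant-medication section), although by ATC code and name, without dose change or time window.

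This objection stands, and it narrows the gap to dose increases of MTX, AZA or MMF already being taken. For these drugs Table 4 gives upper limits, bars initiation and encourages tapering, but does not carry the explicit bar on increases that it gives for corticosteroids. An increase within the limits would not clearly be flagged as a deviation.

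It is also fair to say that the protocol clause is defective. It measures an increase of immunosuppressive treatment against the corticosteroid dose at Week 12, so it could be meant as an immunosuppressant rule or a steroid rule, or be a drafting error. That is a good reason to reword it. It does not justify dropping it without a word in Section 7.

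Finally, treatment failure is an exploratory frequency table, and restoring the component would change no BICLA or SRI-4 responder. That is correct and limits the weight of the point.

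**Conclusion.** The point holds in a limited form. The SAP's treatment-failure definition is narrower than the protocol's, the change is undeclared, and redundancy with BICLA and LLDAS does not hold for Weeks 12 to 24. The specific loss is a dose increase of existing MTX, AZA or MMF in those 12 weeks, half of the protocol clause's window. The SAP is also inconsistent with itself, since 2.2.3 and 4.1.3 keep an objective and endpoint that have no analysis.

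Two further inferences go too far. One is that failure is understated most in the arm that escalates more, so that the comparison is biased in a known direction. The documents contain no escalation rates, so the direction is unknown. The other is that every immunosuppressant increase without a steroid trigger is lost. From Week 24 to Week 36 such an increase makes the patient a BICLA non-responder. The co-primary tests, their error rates and the sample size are unaffected.

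The conclusion assumes that the protocol clause was meant to count immunosuppressant increases, as its opening words say, and that the two corticosteroid grounds are applied alike under both documents.

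**What to change.** Reconcile Protocol 13.9.6 with SAP 2.2.3, 4.1.3, 5.2.4.5.4 and 7.2.2 before database lock and unblinding:

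1. In SAP 5.2.4.5.4, restore an immunosuppressant-increase component for Weeks 12 to 36, measured against each immunosuppressant's own Week 12 level. Do not paste back the protocol wording, because its reference to the corticosteroid dose cannot be applied. State how a newly started drug is treated. Record the rewording in Section 7.
2. Reinstate the frequency table, by arm, of patients with any increase or addition of lupus therapy. The protocol gives it no window, so the SAP should state one; a split at Week 24 would show the period that BICLA does not cover.
3. If the component is removed on purpose, declare that in Section 7 with a reason other than redundancy, and bring the objective and endpoint lists into line.

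This concerns only what is counted, not which treatment is permitted. The cost is SAP wording and one table: medication doses and dates are recorded at each visit (Protocol 11.4.4), and medical review is already planned for both endpoints.
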